### **2.5.2 Statistical hypothesis, model, and method of analysis**

In the primary analysis, the ARR will be estimated by a negative binomial regression model with log-link function, the cumulative number of confirmed MS relapses per subject as the response variable, number of relapses in previous year, baseline EDSS, baseline number of T1 Gd-enhancing lesions and baseline age as continuous covariates. Natural log of time on study in years will be used as the offset variable to account for the varying lengths of subjects' time in the study. The adjusted ARR (i.e., model-based estimate adjusted for covariates) and the corresponding 95% confidence interval will be obtained.

In case of non-convergence, continuous covariates may be removed from the regression model in the order of: baseline EDSS, number of relapses in the previous year, baseline age.

### **2.5.3 Handling of missing values**

For participants who withdraw early from the study, the number of relapses up to the study discontinuation will be used for the primary analysis. No imputation will be applied to the incomplete study duration.

The primary negative binomial regression model with an offset for the time in study adjusts for missing information (drop-out) under the assumption of non-informative drop-out, information is missing at random, and constant relapse rate over time.

### **2.5.4 Supportive analysis**

The primary analysis will be repeated based on all reported MS relapses (confirmed and unconfirmed) for FAS population.

ARR time-based and ARR participant-based will be provided for confirmed relapses and then for all relapses (confirmed and unconfirmed). ARRs using a “time-based approach” are calculated by taking the total number of relapses observed for all subjects divided by the total number of days in study of all subjects and multiplied by 365.25 days. “Participant-based approach” is calculated in the way where individual ARRs are computed and summarized over all subjects.

Listings of relapses along with their confirmation status (confirmed or unconfirmed) will be presented.

## 2.6 Analysis supporting secondary objectives

All analyses for secondary efficacy objectives will be conducted using the FAS.

For MRI related analysis, all available data from scheduled scans will be included, i.e. also including the ones taken in Post-treatment Follow-up period for the prematurely discontinued participants.

### 2.6.1 Secondary endpoint(s)

Secondary efficacy endpoints include:

- To estimate the number of Gd-enhancing T1 lesions per scan, below variables will be derived:
  - The total number of Gd-enhancing T1 lesions will be derived by taking the sum of number of Gd-enhancing T1 lesions from all scheduled MRI scan with a non-missing value. Any Gd-enhanced T1 data obtained less than 30 days after the termination of steroid therapy which is used to treat MS relapses will not be included in analysis of Gd-enhancing T1 lesion related endpoint.
  - The number of MRI scans will be derived by counting the number of scheduled MRI scans with non-missing values for the number of Gd-enhancing T1 lesions (i.e., the number of scans contributed to the derivation of the total number of Gd-enhancing T1 lesions above). Scans obtained less than 30 days after the termination of steroid therapy which is used to treat MS relapses will not be included.
- To estimate annualized rate of new or enlarged T2 lesions, below variables will be derived:
  - The total number of new or enlarged T2 lesions will be derived by taking the number of new or enlarged T2 lesions from last available scheduled MRI scans (relative to the baseline scan) with a non-missing value.
  - The time (in years) from screening scan will be calculated as (date of last scheduled MRI scan with a non-missing value for the number of new or enlarging T2 lesions – date of screening scan +1)/365.25.
- Total T2 lesion volume. Change and % change from baseline will only be defined for subjects with both baseline and post-baseline values and will be calculated as:  
change from baseline = post-baseline value – baseline value;  
% change from baseline = change from baseline / baseline value\*100.

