contraindication for the use of an inactivated, viral-vector-, or mRNA based Sars-CoV-2 vaccine in participants who are immunocompromised. However, different Sars-CoV-2 vaccines may have various mechanisms of action and different associated potential risks. Local prescribing information of any specific Sars-CoV-2 vaccine must be reviewed and local prescribing information requirements for specific contraindications and special warnings and precautions for use must be followed. Vaccination against Sars-CoV-2 during whole study course should be considered on a case-by-case basis at the discretion of the treating physician taking into account the individual benefit-risk assessment and local vaccination recommendations. For details, refer to [Section 16.4.4](#).

15. Have been treated with any other MS DMT within 5 elimination half-lives (according to their labels) or within expected pharmacodynamic effect window. For the medications commonly used in MS treatment, wash-out period is suggested to be:

Medication	Exclusionary if used/used within required wash-out period
Systemic corticosteroids, adrenocorticotropic hormone	30 days prior to Screening MRI scan
interferon- β or glatiramer acetate	none
Intravenous immunoglobulin	8 weeks prior to baseline
Plasmapheresis	8 weeks prior to baseline
Siponimod and ponesimod	4 weeks prior to baseline
Fingolimod	8 weeks prior to baseline
Teriflunomide	3.5 months prior to baseline or 1 month prior to baseline if participant undergoes AEP (Accelerated Elimination Procedure) before baseline
B-cell targeted therapies (e.g., rituximab, ocrelizumab, obinutuzumab)	Prior to consideration for trial/at Screening, B-cell recovery (LLN as per central lab) needs to be verified and documented by the investigator Or 2 years prior to baseline
BTK inhibitors	2 weeks prior to baseline
Natalizumab (Participants who have discontinued natalizumab in the 6 months prior to randomization should be evaluated to rule out PML)	12 weeks prior to baseline
Mild to moderately immunosuppressive/chemotherapeutic medications (e.g. azathioprine, methotrexate)	24 weeks prior to baseline
Highly immunosuppressive/chemotherapeutic medications (e.g., mitoxantrone, cyclophosphamide, cladribine)	48 weeks prior to baseline
Alemtuzumab	Anytime
Lymphoid irradiation or bone marrow transplantation	Any time
Mitoxantrone (with evidence of cardiotoxicity following treatment or cumulative life-time dose > 60 mg/m ²)	Anytime
Ofatumumab	Anytime

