6.2.1.1 Permitted concomitant therapy requiring caution and/or action

Only limited benefit of premedication with steroids, antihistamines, or acetaminophen was seen in RMS clinical studies (refer also to the Investigator's Brochure). Injection-related reactions (systemic or local reactions) can be managed with symptomatic treatment, should they occur. If Investigators choose to administer premedication, it should be administered 30 to 60 min prior to study drug injection. Any administrations of premedication must be recorded in the appropriate eCRF.

A standard short course of intravenous corticosteroids (methylprednisolone) is allowed for the treatment of MS relapses (refer to [Section 6.2.3](#)). In addition, the restrictions regarding MRI assessments during, or within 30 days after termination of steroid therapy, must be followed ([Section 8.3.2](#))

The medications allowed for treatment of adverse reactions and MS relapses are not considered study supplies, and therefore, need to be supplied by the study site.

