During the study, the quality of each scan performed on scheduled visits will be assessed by the central MRI reading center. The MRI scan should be sent to the central MRI reading center upon completion. As soon as the scan is received by the central MRI reading center, it will be evaluated for quality, completeness and adherence to the protocol. Confirmation of MRI quality or a description of the quality problems, if detected, will be communicated to the site. If a scan is incomplete or incorrectly performed, the study center will be asked to repeat it as soon as possible. After completion of the quality check, all scans will be analyzed according to the MRI manual.

As per [Section 4.6](#), during a Public Health Emergency as declared by local or regional authorities i.e. pandemic, epidemic, or natural disaster, that limits or prevents on-site study visits, the collection of images may be modified by Novartis and will be communicated to the Investigator.

Restrictions for MRI schedule

To avoid potential interference caused by steroids used for the treatment of MS relapses, the following restrictions will be applied for this study:

- In case of relapse, if an MRI would have been scheduled within 30 days of the initiation of steroid treatment, this MRI should be performed before steroid treatment is initiated
- No MRI scan should be performed while a participant is on steroid therapy and within 30 days after termination of steroid therapy

8.3.3 Efficacy assessment 3

Expanded Disability Status Scale (EDSS) will be determined, based on neurological examination at scheduled visits ([Table 8-1](#) and [Table 8-2](#)) and in case of a suspected MS relapse.

The EDSS is an ordinal scale used for assessing neurologic impairment in MS based on a neurological examination. It consists of scores in each of seven functional systems (FSs) that are then combined to determine the EDSS steps [ranging from 0 (normal) to 10 (death due to MS)]. The FSs are Visual, Brain Stem, Pyramidal, Cerebellar, Sensory, Bowel & Bladder, and Cerebral functions (fatigue contributes). The FSs and EDSS steps will be assessed in a standardized manner. EDSS is a widely used and accepted instrument to evaluate disability status at a given time and, longitudinally, to assess disability progression in clinical studies in MS.

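### The SAP's steroid exclusion for the Gd endpoint covers only relapse steroids, so scheduled scans taken after a systemic corticosteroid course for another reason stay in the analysis

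*SAP*

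**What the plan says.** SAP section 2.6.1 builds the Gd endpoint from two derived variables, and each has a steroid rule. The lesion total leaves out "Any Gd-enhanced T1 data obtained less than 30 days after the termination of steroid therapy which is used to treat MS relapses". For the scan count, which becomes the offset, the rule is "Scans obtained less than 30 days after the termination of steroid therapy which is used to treat MS relapses will not be included". Both depend on the reason for the steroid. Outside these rules SAP section 2.6 states that "all available data from scheduled scans will be included", including follow-up scans of participants who stopped early. No other SAP rule removes a scan because of steroid use.

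The protocol has two broader statements. Exclusion criterion 15 lists "Systemic corticosteroids, adrenocorticotropic hormone" with the period "30 days prior to Screening MRI scan" and names no indication. In section 8.3.2, under the restrictions for the MRI schedule, the second bullet reads "No MRI scan should be performed while a participant is on steroid therapy and within 30 days after termination of steroid therapy", again without an indication. The sentence introducing that bullet, however, gives its purpose as avoiding interference from steroids used for relapses.

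On study, Table 6-2 prohibits systemic corticosteroids alongside study treatment except for relapses or as premedication. The action listed is interruption of study treatment; MRI data are not mentioned. Section 6.2.1.1 leaves premedication to the investigator: "If Investigators choose to administer premedication, it should be administered 30 to 60 min prior to study drug injection".

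**The concern.** Whether a scan is analysed depends on why the steroid was given, not on whether it was given. The protocol's washout before the Screening MRI makes no such distinction. The baseline Gd count is a covariate in the Gd model (SAP section 2.6.2), so covariate and outcome are protected to different standards.

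The direction of any effect is the reason to act. Section 8.3.2 of the protocol restricts MRI timing because steroids can interfere with the reading. If a non-relapse course lowers the number of enhancing lesions on a retained scan, the estimated lesions per scan falls. In a single-arm study no control group shares that effect, so it would be read as an effect of ofatumumab.

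**Working it through.** No planned figure depends on this rule, so there is none to reproduce. The check has three parts: which scans the rules cover, how scans fall relative to injections, and how a bias would scale.

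**1. Coverage, case by case**

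| Steroid use before a scheduled post-baseline scan | Protocol position | SAP 2.6.1 |
|---|---|---|
| Relapse course ended less than 30 days earlier | Scan barred by 8.3.2 | Scan dropped |
| Relapse course still running | Scan barred by 8.3.2 | Not expressly dropped; the window starts at termination |
| Non-relapse course during treatment | Prohibited by Table 6-2; scan barred only if the 8.3.2 bullet is read literally | Scan kept |
| Non-relapse course after early discontinuation, before a follow-up scan | Outside Table 6-2, which applies alongside study treatment; scan barred only on the literal reading | Scan kept |
| Premedication at an injection | Permitted (6.2.1.1, Table 6-2) | Scan kept |

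The fourth row arises because Protocol Table 8-2 asks for an end-of-follow-up MRI in early discontinuers with no scan in the last 3 months, and SAP 2.6 analyses those scans.

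**2. Timing of premedication**

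Injections are due on Days 0, 7 and 14, on Day 28, and every 28 days to Day 308, with none at Month 12 (Protocol section 6.3.2 and Table 8-1). Treatment-period scans are targeted at Days 84 and 336 (SAP Table 2-3).

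- Month 3: 84 − 56 = 28 days after the preceding injection (the fifth).
- Month 12: 336 − 308 = 28 days after the preceding injection (the fourteenth).
- Premedication at the first four injections only: 84 − 28 = 56 days, outside a 30-day window.
- An on-schedule injection followed by a scan two days late: 28 + 2 = 30 days, also outside a rule of less than 30 days.

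So only premedication at the Day 56 or Day 308 injection places an on-schedule scan inside the window, by two days.

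**3. Scaling of a bias**

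Let f be the share of analysed scans under a non-relapse steroid effect and s the fractional lowering of the count on those scans. If affected and unaffected scans would otherwise have the same mean, the relative bias in lesions per scan is about −f × s. The documents give neither quantity, so every value here is an assumption.

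| f | s = 20% | s = 50% | s = 80% |
|---|---|---|---|
| 5% | −1.0% | −2.5% | −4.0% |
| 10% | −2.0% | −5.0% | −8.0% |
| 20% | −4.0% | −10.0% | −16.0% |
| 30% | −6.0% | −15.0% | −24.0% |

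The lower two rows should not be used for the gap described here. Prohibited courses are unlikely to reach 20% of scans. Premedication might, but then nothing in the documents supports the suppression values.

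**The case against.** The strongest reply is that the SAP does what the protocol asks. The lead-in to the MRI restrictions in section 8.3.2 names relapse steroids as the source of interference, and SAP 2.6.1 uses the same limit. That stands: a reader might infer that the SAP contradicts the protocol, but it departs only from the literal wording of one bullet. If that bullet is read literally, the scans in question are already barred at the site, and only those done despite it reach the analysis.

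It also stands that non-relapse courses are prohibited on treatment and should be rare. The baseline asymmetry has limited force too. The endpoint is a post-baseline count per scan, not a change from baseline. The Screening MRI can itself establish eligibility through Gd positivity (inclusion criterion 3), which is a separate reason for a stricter rule there.

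From the 28-day spacing a reader might infer that steroid premedication contaminates the post-baseline Gd scans generally. The documents do not support this. Premedication is optional, the protocol reports little benefit from it, and only two injections matter for on-schedule scans. Nothing shows that a single dose before an injection suppresses enhancement 28 days later.

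The reply does not cover the remaining case. A scan taken after a non-relapse course, whether through a deviation or in follow-up of an early discontinuer, is analysed with no rule to remove or flag it.

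**Conclusion.** The point holds as a gap in the SAP's exclusion rule and as an asymmetry with the Screening washout. It concerns systemic corticosteroid courses given for reasons other than relapse, together with scans taken while a course is running. Any bias would make the Gd result look better for ofatumumab. Its size cannot be derived from the documents; with 5% of scans affected it would be 1% to 4% under the assumed suppression of 20% to 80%, and the true share may be smaller.

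The consequence is limited to one secondary endpoint in a study that tests no hypotheses. The primary annualized relapse rate does not use MRI scans as outcome data and is unaffected. The case for changing the text rests on the low cost and the known direction of the bias, not on a demonstrated large effect.

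**What to change.** In both sentences of SAP 2.6.1 (lesion total and scan count), replace the limit to relapse treatment with any systemic corticosteroid course recorded as concomitant medication, other than injection premedication. Also exclude scans taken during such a course, so that the window no longer begins only at termination. This is a change to the analysis rule and alters no trial procedure.

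The data are already collected: the protocol has all medications after enrollment recorded (section 6.2.1), and concomitant medications remain on the follow-up schedule (Table 8-2). The cost is the wording and the loss of a few scans. A participant left with no eligible scan would drop out of the Gd model.

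Optionally, add one supportive Gd model that also drops scans less than 30 days after steroid premedication, using the steroid category and premedication subcategory already defined in SAP section 2.4.2.3. This should stay supportive. In the main analysis it would remove both on-schedule treatment-period scans of anyone premedicated with steroids at every injection, for an effect that the documents do not establish.

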### 2.6.2 Statistical hypothesis, model, and method of analysis

Methods of analyses for efficacy endpoints defined in [Section 2.6.1](#) are described below.

- The number of Gd-enhancing T1 lesions per scan will be estimated by a negative binomial regression model with log-link function, the total number of Gd-enhancing T1 lesions during (per subject) as the response variable. Natural log of the number of MRI scans will be used as the offset. The model will include baseline age and number of Gd-enhancing T1 lesions at baseline as continuous covariates. The estimated number of Gd-enhancing T1 lesions per scan will be obtained together with the corresponding 95% confidence interval.

In case of non-convergence, continuous covariates may be removed from the regression model in the order of number of Gd-enhancing T1 lesions at baseline and baseline age.

**Supportive analyses:** descriptive summary statistics (mean, median, standard deviation, min, max) for the number of Gd-enhancing T1 lesions per scan will be provided by visit. Number and percentage of subjects free of Gd-enhancing T1 lesions will also be provided.

- The annualized rate of new or enlarged T2 lesions will be estimated by a negative binomial regression model with log-link function, the total number of new or enlarged T2 lesions (relative to baseline scan, per subject) as the response variable. Natural log of time from screening scan in years will be used as the offset. The model will include baseline age and baseline volume of T2 lesions as continuous covariates. The estimated number of new or enlarged T2 lesions will be obtained together with the corresponding 95% confidence interval.

In case of non-convergence, continuous covariates may be removed from the regression model in the order of baseline volume of T2 lesions and baseline age.

**Supportive analyses:** descriptive summary statistics (mean, median, standard deviation, min, max) for the number of new or enlarged T2 lesions will be provided by visit. Number and percentage of subjects free of new or enlarged T2 lesions will also be provided.

Above analyses will also be repeated to assess new or enlarged T2 lesions after onset period (EOS scan relative to Month 3 scan).

Note: new or enlarged T2 lesions after onset period (EOS scan relative to Month 3 scan) will be derived as the new or enlarged T2 lesions at EOS scan (relative to baseline scan) subtracting that at Month 3 scan (relative to baseline scan). If a negative value is obtained, then 0 will be used. i.e.

$$neT2_{EOS \text{ rel } M3} = \max(neT2_{EOS \text{ rel } BL} - neT2_{M3 \text{ rel } BL}, 0)$$

- Descriptive summary statistics (mean, median, standard deviation, min, max) will be provided by visit for the change and % change in total volume of T2 lesion.

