12.5 Analysis supporting secondary objectives

12.5.1 Efficacy and/or Pharmacodynamic endpoint(s)

The following MRI efficacy variables will be analyzed based on FAS:

- The analysis of the number of Gd-enhancing T1 lesions per MRI-scan will be done using a negative binomial regression model with log-link function. The total number of Gd-enhancing lesions (cumulative count of Gd-enhancing lesions across all the MRI-scans per participant) will be used as the response variable, using baseline age and baseline number of Gd-enhancing T1 lesions as continuous covariates. Natural log of the number of MRI-scans will serve as the offset variable to account for the varying lengths of participants' time in the study. The number of Gd-enhancing lesions per scan will be estimated and the corresponding 95% confidence interval will be obtained.
- The analysis of the annualized rate of new or enlarging T2 lesions will be done using a negative binomial regression model with log-link function. The number of new or enlarging T2 lesions on the last available MRI scan relative to baseline will be used as the response variable, using baseline age and baseline volume of T2 lesions as continuous covariates. Natural log of the time (in years) of the MRI-assessment from the baseline/Screening scan will serve as the offset variable to account for the varying lengths of participants' time in the study. The number of new or enlarging T2 lesions per year will be estimated and the corresponding 95% confidence interval will be obtained.
- Change from baseline in T2 lesion volume on MRI will be summarized by visit.

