**Table 2-3 Visit-windows for MRI**

Visit-window	Start day	Target Day	End day
Month 3	1	84	210
Month 12	211	336	462

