#### **5.4.2 Analysis supporting secondary objective(s)**

Details to conduct the analysis on the negative binomial regression model are the same as that in the primary objective.

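### The post-onset T2 lesion rate (Month 3 to EOS) has its own count but no matching time offset; with the only offset the SAP defines, the rate comes out about 25-31% too low on schedule

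*SAP*

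**What the plan says.** SAP 2.6.1 defines a single time variable for T2 lesions: "The time (in years) from screening scan will be calculated as (date of last scheduled MRI scan with a non-missing value" for the T2 count, minus the screening scan date, plus one, divided by 365.25). SAP 2.6.2 puts it into the negative binomial model: "Natural log of time from screening scan in years will be used as the offset". Protocol 12.5.1 uses the same starting point: "Natural log of the time (in years) of the MRI-assessment from the baseline/Screening scan will serve as the offset variable".

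At the end of its T2 item, SAP 2.6.2 adds a repeat for the later part of the study: "Above analyses will also be repeated to assess new or enlarged T2 lesions after onset period (EOS scan relative to Month 3 scan"). A note then redefines the response. Post-onset lesions "will be derived as the new or enlarged T2 lesions at EOS scan (relative to baseline scan) subtracting that at Month 3 scan", both counted against baseline, and "If a negative value is obtained, then 0 will be used". The note gives no new time variable.

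The modelling appendix does not supply one. SAP 5.4.2 says only: "Details to conduct the analysis on the negative binomial regression model are the same as that in the primary objective". SAP 5.4.1, to which that points, refers to log time in years without giving a start date for a post-onset interval.

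**The concern.** In a log-link count model, the offset must measure the period in which the counted events could occur. Here the numerator has been cut down to Month 3 onwards, while the only stated denominator still includes the screening period and the first three months. Lesions from those months have been subtracted, but their time has not.

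This undermines the purpose of the analysis. Where the EOS scan is the last scheduled scan, the post-onset and overall rates share a denominator, and the post-onset count can never exceed the overall count. Each such participant's crude post-onset rate is therefore at or below the overall rate by construction, even if lesion activity were constant or rising. A lower rate after onset would then not be evidence of a sustained effect.

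There is a smaller mismatch as well. The redefined count stops at the EOS scan, but the time in SAP 2.6.1 runs to the last scheduled scan. For participants who stop treatment early, that can be a follow-up scan (SAP 2.1 and 2.6; Protocol Table 8-2, footnote 6), which makes the written denominator longer still.

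**Working it through.** The documents give no figure for this analysis, so there is none to reproduce. The check compares the two candidate offsets.

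**Inputs**
- MRI target days: Day 84 (Month 3) and Day 336 (Month 12/EOS), with the Month 12 window ending on Day 462. Source: SAP, "Table 2-3 Visit-windows for MRI".
- Screening scan: Day -30 to Day -1. Source: Protocol Table 8-1.
- Day numbering: first dose is Day 1 and there is no Day 0. Source: SAP 2.1.1.
- Interval convention: end date minus start date plus 1. Source: SAP 2.6.1.

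**Formula.** With offset ln(t), the estimated rate scales as 1/t. So:

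ratio = (Month 3-to-EOS time) / (screening-to-EOS time); shortfall = 1 - ratio.

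**On schedule**
- Interval the count covers: 336 - 84 + 1 = 253 days.
- Written time, screening scan on Day -1: 335 + 1 + 1 = 337 days. Ratio 253/337 = 0.751, shortfall 25%.
- Written time, screening scan on Day -30: 335 + 30 + 1 = 366 days. Ratio 253/366 = 0.691, shortfall 31%.

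For example, one post-onset lesion corresponds to 365.25/253 = 1.44 per year over its own interval. With the written offset it becomes 365.25/337 = 1.08 to 365.25/366 = 1.00 per year.

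Counting first dose as Day 0 instead gives 338 to 367 days and a shortfall of 25.1% to 31.1%, so the day convention hardly matters.

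**Off schedule** (screening scan Day -1 to Day -30; other scan on target)

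| Timing | Ratios | Shortfall |
|---|---|---|
| Month 3 scan on Day 56 | 281/337 to 281/366 | 17-23% |
| Last scan on Day 462 | 379/463 to 379/492 | 18-23% |
| Month 3 scan on Day 112 | 225/337 to 225/366 | 33-39% |
| EOS scan on Day 252 | 169/253 to 169/282 | 33-40% |

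**Model-level check.** Both offsets were fitted to the same simulated counts: 400 runs per setting, 85 participants, screening scan uniform over Day -30 to Day -1, and an assumed true rate of 1.0 lesion per year with dispersion 1.5. The negative binomial model included age and log T2 volume. The median ratio of the two rates was:
- 0.720 with scans on target (95% range 0.715-0.725; 399 runs converged);
- 0.720 with both scans uniform within 14 days either side (0.711-0.728);
- 0.719 within 28 days either side (0.706-0.732).

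If timing varies evenly around the targets, the model rate is therefore about 28% too low. The simulation shows what the written offset does, not which offset was intended. Its counts never fall between scans, so the floor plays no part.

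**The floor at zero.** It raises the mean count and so acts in the opposite direction. To cancel the offset error on schedule, it would have to raise the mean post-onset count by 33% (337/253 = 1.33) to 45% (366/253 = 1.45).

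**The case against.** The strongest reply is that this is an omission rather than a wrong instruction. The screening-scan time was paired with a count taken against baseline. The repeat replaces that count and labels it as EOS relative to Month 3, which names both ends of the interval, and a careful programmer could infer the matching time. The SAP also mentions a dataset specification, cited only for date imputation and not available here, which might state it. This stands in part: a Month 3-to-EOS time may well be intended. But no text in either document says so, the one formula given leads to a different answer, and two competent programmers could differ by a factor of 1.33 to 1.45.

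A second reply is that the repeat may cover only the descriptive summaries that immediately precede it, in which case no offset is involved. That reading is possible. However, the rate model sits in the same T2 item, and the plainer reading includes it.

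Third, the net direction is not proven, because the floor pushes the other way. That is right as far as it goes: the 25-31% is the offset effect alone.

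Fourth, the weight is limited. The post-onset analysis is not a protocol endpoint, the study has one arm, and no hypothesis is tested. This is accepted and is reflected in the verdict.

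**Conclusion.** The concern holds. Read literally, the SAP annualises a Month 3-to-EOS count over the time since the screening scan. The offset alone makes the post-onset rate 25-31% too low, in the drug's favour.

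That range assumes post-baseline scans on Days 84 and 336, a screening scan within Day -30 to Day -1, and EOS as the last scheduled scan. It is not a bound. Off-schedule scans move it to between 17% and 40% in the cases above. A screening MRI carried over at re-screening (Protocol 8.1 allows one up to 3 months old) would enlarge it. The relative size does not depend on the true lesion rate.

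This should be corrected, but its reach is narrow. One model-based estimate and its confidence interval change in a repeat of a secondary-endpoint analysis, and the study's main conclusions do not. The documents do not say how the post-onset rate will be used.

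**What to change.** Add to the note on the post-onset derivation in SAP 2.6.2:

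*For this analysis the offset is ln[(EOS scan date - Month 3 scan date + 1)/365.25], in participants with non-missing counts at both scans.*

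This matches the denominator to the numerator and ends both at the EOS scan, so follow-up scans no longer lengthen the time. On schedule the estimated rate rises by a factor of 1.33 to 1.45 compared with the written offset. Restricting to participants with both scans adds little that is new, since the count is a difference of two scans and SAP 2.6.3 rules out imputation.

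The cost is one sentence in the SAP and the matching line in the dataset specification. No new data are needed, because both scan dates are already collected.
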